AIM-HN is based on a two-stage minimax design with a hypothesized ORR of $p_1=30\%$ for tipifarnib and a minimal or uninteresting ORR of $p_0=15\%$. The primary efficacy analysis, based on the evaluation of a 2-sided 95% confidence interval around the ORR, will be performed on the mITT population comprised of all enrolled subjects who have received at least one dose of tipifarnib through their participation in AIM-HN. The mITT will also be used for all safety analyses.

AIM-HN plans to enroll at least 80 subjects with HRAS mutations [REDACTED]
[REDACTED]
meeting all criteria for inclusion in the per-protocol analysis set. [REDACTED]
[REDACTED]
[REDACTED]
[REDACTED]
[REDACTED]
[REDACTED]
[REDACTED]

[REDACTED]
[REDACTED]
[REDACTED]
[REDACTED]
[REDACTED]
[REDACTED]
[REDACTED]
[REDACTED]
[REDACTED]
[REDACTED]
[REDACTED]
[REDACTED]
[REDACTED]
[REDACTED]

The final analysis will be conducted on all subjects in the mITT analysis population set as well as the planned 80 subjects in the per-protocol analysis set.

[REDACTED]

STUDY ASSESSMENTS:

Table 1: Schedule of Events: Pre-screening for HRAS Mutations

Activity	Pre-Screening ¹
ICF for Pre-screening for HRAS mutations	X
Tumor tissue for HRAS mutational testing ²	X
HRAS mutation information ⁴	X
Collection of first line efficacy/response data and demographics	X

Upon determination of HRAS mutational status, subject will proceed to cohort-specific screening procedures for participation in AIM-HN (HRAS mutant HNSCC subjects, refer to Table 2) or SEQ-HN (HRAS wildtype HNSCC subjects, refer to Table 3)

1. Pre-screening for HRAS mutation procedures can be done at any time prior to enrollment in AIM-HN or SEQ-HN.
2. Required for subjects with unknown HRAS mutational status. Tumor tissue for HRAS testing should be on a biopsy taken subsequent to the most recent prior therapy so that the most current tumor biology is assessed; if a biopsy meeting this criterion is not possible, the reason must be documented. Detailed tumor sample collection, storage and shipping procedures will be provided in a separate lab manual. Results must be obtained prior to enrolment in either cohort. Further collection of tissue may be requested from wildtype patients.
3. [REDACTED]

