7. Buccal swabs will be collected at screening for CXCL12 SNP testing and as a control sample for the analysis of tumor mutations using kits provided by the Sponsor. If swabs are not collected during screening for any reason, collection can be conducted at any time during the study. Detailed buccal swab collection, storage and shipping procedures will be provided in a separate lab manual.
8. Assessments of adverse events and concomitant medications may also be conducted if adverse events were not resolved at the time of the End of Treatment visit.
9. Assessed from signing the AIM-HN ICF through approximately 30 days after treatment discontinuation. Additional assessments may be performed until AE resolution or the AE is deemed irreversible by the Investigator.
10. Evaluation should be performed within 14 days prior to the first administration of study drug. Lab investigations (hematology and serum chemistry) should be repeated and reviewed within 72 hours of first dosing and continued eligibility for dosing confirmation.
11. Assessment on Cycle 1 Day 1 is to occur prior to tipifarnib dosing. Labs drawn within 72 hours of dosing may be used for CID1. Labs must be reviewed prior to dosing to confirm subject remains eligible.
12. Vital signs to include: heart rate, blood pressure and temperature.
13. In addition to baseline tumor scans that are to be obtained within 28 days prior to Cycle 1 Day 1, efforts should be made to obtain historical scans to document tumor progression on prior line of therapy for transfer to the IRF. All efforts to submit these scans by the first tumor response assessment (approximately 8 weeks following Cycle 1 Day 1) should be made. These historical scans should include the scans that demonstrate progression that occurred on the prior regimen and a prior scan demonstrating the nadir prior to the progression.
14. Pregnancy testing will be performed in females of child-bearing potential and testing may be performed on urine or serum. If a positive urine pregnancy test is obtained, a confirmatory serum pregnancy test should be conducted. If confirmatory test is positive, subject must terminate tipifarnib treatment immediately and follow pregnancy reporting guidelines outlined in the protocol. Pregnancy testing will be performed locally at the clinical site or its reference laboratory.

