9.1.1 Subjects With Known HRAS Mutation

If a subject has had HRAS mutation testing as part of their medical care or through another study protocol, the following circumstances need to be considered prior to enrolment into the AIM-HN part of KO-TIP-007:

- If HRAS mutation data were obtained subsequent to the most recent prior therapy, and obtained using a Sponsor approved test, these data may be used for enrollment. Re-biopsy should be considered for tumor tissue not meeting this requirement. If re-biopsy is not possible, the clinical justification should be recorded. Procedures as outlined in [Section 9.1.2](#) regarding obtaining tumor material for potential confirmatory testing at a central laboratory should be followed.
- If HRAS mutation data were obtained using a test which is not approved by the Sponsor, these data may not be used for enrollment. In such cases, HRAS testing procedures outlined in [Section 9.1.2](#) should be followed for study eligibility.

In addition, the following procedures are to be performed in all subjects with known HRAS mutation status irrespective of method for previous HRAS testing:

- ICF for HRAS pre-screening: Subjects must be consented for study participation and should be documented in the subject's medical chart.

- Collection of a blood sample for the analysis of HRAS mutations [REDACTED] [REDACTED] in plasma and shipment to a Sponsor designated laboratory.
- Collection of HRAS mutation data including:
 - Anatomical biopsy site, date of sampling and setting (e.g. primary, locally advanced, metastatic lesion)
 - HRAS mutation in sample including variant allele frequency or HRAS wildtype status
 - Test platform (e.g. NGS, PCR, other)

9.1.2 Subjects Without Known HRAS Mutational Status: Testing for HRAS mutation at a Sponsor Designated Laboratory

The following procedures must be performed:

- ICF for HRAS pre-screening: Subjects must be consented for study participation and should be documented in the subject's medical chart.
- Collection and shipment of tumor material for HRAS mutation testing at a Sponsor designated laboratory. Additional details regarding HRAS testing procedures will be provided in a separate laboratory manual.
- Collection of a blood sample for the analysis of HRAS mutations [REDACTED] [REDACTED] in plasma and shipment to a Sponsor designated laboratory.
- Collection of HRAS mutation data including:

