11 ASSESSMENT OF SAFETY

The following subsections apply only to subjects participating in AIM-HN.

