11.3 Adverse Event Reporting

11.3.1 Procedure for Reporting Adverse Events

The AE reporting period for safety surveillance begins when the subject is included into the study (date of first signature of AIM-HN informed consent) and continues through the study's post-treatment follow-up period, defined as approximately 30 days from the final administration of the study treatment or immediately before initiation of any other anticancer therapy, whichever comes first.

The Investigator is required to grade the severity/intensity of each AE. Investigators will reference the NCI-CTCAE v 5.0. This is a descriptive terminology that can be used for AE reporting. A general grading (severity/intensity) scale is provided at the beginning of the referenced document, and specific event grades are also provided. If a particular AE's severity/intensity is not specifically graded by the guidance document, the Investigator is to revert to the general definitions of Grade 1 through Grade 5 and use his or her best medical judgment.

The 5 general grades are:

- Grade 1: Mild

- Grade 2: Moderate
- Grade 3: Severe or disabling
- Grade 4: Life-threatening
- Grade 5: Death related to AE. Note: Death (Grade 5 as defined by NCI-CTCAE version 5.0) is mainly regarded as an outcome, to be documented as described below.

According to the Sponsor's convention, if a severity/intensity of Grade 4 or 5 is applied to an AE, then the Investigator must also report the event as an SAE as per [Section 11.4.2](#). However, a laboratory abnormality with a severity/intensity of Grade 4, such as low white blood cell count or increased ALT, is considered serious only if the condition meets one of the serious criteria described below.

In the case of death, the primary cause of death (the event leading to death) should be recorded and reported as an SAE. "Fatal" will be recorded as the outcome of this respective event; death will not be recorded as separate event. Only if no cause of death can be reported (e.g., sudden death, unexplained death), the death per se might be reported as an SAE.

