11.4.4 Events Not to Be Considered as AEs/SAEs

Medical conditions present at the initial study visit that do not worsen in severity or frequency during the study are defined as Baseline Medical Conditions and are NOT to be considered AEs. Progression of underlying disease is not an AE and therefore not an SAE per se, rather an efficacy endpoint, unless deemed to be causally related to administration of IP. However, if

adverse signs or symptoms occur in association with disease progression then these should be recorded as AEs and reported as SAEs if meeting any seriousness criteria.

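### A complication of a biopsy done for HRAS pre-screening has no defined sponsor AE/SAE route before AIM-HN consent

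*Protocol*

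**What the plan says.** **Tissue at pre-screening**
- Protocol Table 1, footnote 2: "Tumor tissue for HRAS testing should be on a biopsy taken subsequent to the most recent prior therapy". The exception follows: "if a biopsy meeting this criterion is not possible, the reason must be documented". Section 9.1 words the same point as a recommendation.
- Section 9.1.1, for patients whose HRAS mutation is already known: "Re-biopsy should be considered for tumor tissue not meeting this requirement".
- Table 1, footnote 2, for patients without the mutation: "Further collection of tissue may be requested from wildtype patients".
- Sections 9.1.1 to 9.1.3 also require a blood sample at pre-screening, and 9.3.3 takes another during SEQ-HN.
- Pre-screening consent is separate from cohort consent (9.2.1, 9.3.1).

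**Safety collection**
- Table 2, footnote 9, on AEs: "Assessed from signing the AIM-HN ICF through approximately 30 days after treatment discontinuation".
- Section 11.3.1 defines the start of the reporting period as the "date of first signature of AIM-HN informed consent". Section 11.1 uses the same start, and 11.3.2 limits SAE reporting to that period.
- The opening of Section 11: "The following subsections apply only to subjects participating in AIM-HN".
- Section 11.4.4 classes as Baseline Medical Conditions, not AEs, "Medical conditions present at the initial study visit that do not worsen in severity or frequency during the study".

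**The concern.** The study encourages a procedure under one consent and opens its safety window under a later one. The protocol itself recognises the hazard: the AIM-HN design text and Section 9.1 both give excessive biopsy risk as a reason for using older tissue. Some of those biopsied will never be offered tipifarnib here, because their tumour is wild-type.

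If complications in these patients have no route to the sponsor, the IDMB and the clinical study report have no systematic basis for judging the risk of the tissue strategy. What is at stake is safety oversight of a study procedure. The efficacy result and the safety profile of tipifarnib are not in question.

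**Working it through.** The plan gives no figure to reproduce. The check sets the consent sequence, the tissue rules and the reporting window side by side.

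1. **When can a study-driven biopsy occur?** At any time before treatment, including during first-line therapy (9.1). It can therefore fall well before AIM-HN consent.

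2. **When does the window open?** At AIM-HN consent, in Table 2 footnote 9, 11.1 and 11.3.1 alike. SAEs follow the same period (11.3.2).

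3. **Is there another route?** As legible, Table 1 (pre-screening) and Table 3 (SEQ-HN) have no AE row, and Sections 9.1 and 9.3 describe no AE or SAE procedure.

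4. **What happens to each kind of patient?**

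| Patient and timing | Route on the legible text |
|---|---|
| Wild-type, whether or not in SEQ-HN | None defined; outside Section 11 |
| Mutation found, but ineligible for or declines AIM-HN | None defined for an event before AIM-HN consent |
| Enters AIM-HN, complication resolved before consent | Outside the window |
| Enters AIM-HN, complication still present | Ongoing events are assessed at screening (9.2.1), but 11.4.4 may make it a Baseline Medical Condition unless it worsens |
| Biopsy after AIM-HN consent | Inside the window |

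5. **Would the analysis pick it up?** SAP 9.8.1 bases AE summaries, unless otherwise indicated, on events starting on or after first dose. A pre-screening complication is not among them.

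6. **Is study entry defined consistently?** No. Section 6.9.1 ties enrolment in the study to pre-screening consent, whereas 11.3.1 equates inclusion with AIM-HN consent. SAP 9.1 adds a third definition: consent plus meeting the entry criteria of either cohort. This matters for 11.4.4, because which visit is the initial one depends on the definition chosen.

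7. **Context only.** The planned minimum is 80 + 225 = 305 subjects, and 225 / 305 = 73.8% of them are in SEQ-HN, where no AE procedure is described. This is not a count of biopsies. The documents do not give the number pre-screened, the share with a biopsy done for the study, or a complication rate.

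**The case against.** A reader might infer more than the text supports, and the case against those stronger readings is good.

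- **That biopsy harm is never captured.** The documents do not say so. AIM-HN screening assesses ongoing events (9.2.1), and 11.4.4 exempts a baseline condition only while it does not worsen. The subject file is to hold all AEs observed (6.9.3), and investigators must notify the IRB/IEC of SAEs as local procedures require (13.1). This stands. None of these provisions, however, gives the sponsor a reporting pathway for a patient who never enters AIM-HN.
- **That a new biopsy is compulsory.** It is not. Tissue already taken after the last therapy in routine care qualifies, and an exception needs only a documented reason.
- **That re-biopsy is urged on everyone, including wild-type patients.** The re-biopsy sentence is in 9.1.1 and concerns known HRAS results before AIM-HN entry. The request for further wild-type tissue does not say that a new biopsy is meant.
- **That 11.4.4 necessarily removes these events.** If the initial study visit is the pre-screening visit, a later complication was not present then. The text is unclear, so the safe statement is that the event may be treated as baseline.
- **That a number of lost events can be given.** Every rate needed would be assumed.

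Parts of Tables 1 and 3 are blacked out and the pre-screening consent form is not available, so the absence of an AE row is a finding on legible text only. The start date in 11.3.1 and the scope sentence of Section 11 are explicit and do not depend on the redacted parts.

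**Conclusion.** The concern holds in limited form. Followed as written, the reporting rule leaves a complication of a biopsy done for KO-TIP-007 before AIM-HN consent without a defined sponsor AE/SAE route in patients who are wild-type, ineligible or decline AIM-HN. In AIM-HN entrants, capture is incomplete and depends on how 11.4.4 is read. The conflict between 6.9.1 and 11.3.1 over when a subject joins the study needs reconciling in any case.

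The size cannot be stated. The conclusion assumes only that some biopsies are done because of the study and before AIM-HN consent, and that the redacted cells do not contain a separate pathway. The ORR analysis is untouched. This is an inexpensive improvement to safety oversight and does not threaten the trial's conclusions.

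**What to change.** From signature of the pre-screening consent, collect only those AEs and SAEs that the Investigator attributes to a biopsy or blood draw performed specifically for KO-TIP-007. Exclude standard-of-care procedures and archival tissue. Apply this to all pre-screened and SEQ-HN subjects, for a fixed window after each procedure that the protocol states (for example 30 days).

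Do not collect all-cause SAEs outside AIM-HN. At least 225 SEQ-HN patients may be on standard therapy, and an open-ended rule would bring their disease and treatment events under 24-hour reporting.

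To avoid a new contradiction, make these changes together:
- the scope sentence of Section 11, then 11.1, 11.3.1 and 11.3.2;
- 11.4.4, stating that these procedure-related events are not reclassified as baseline conditions;
- Table 2 footnote 9, and an AE entry in Tables 1 and 3;
- 11.4.1, whose AE definition and relatedness categories are framed around a pharmaceutical product, so that attribution to a procedure can be recorded;
- 6.9.1 and 11.3.1, so that study entry has one meaning.

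List the events in the clinical study report separately from treatment-emergent AEs. SAP Section 3 refers to early closure of the study. If pre-screening has ended, the sponsor can query sites retrospectively and state the limitation in the report.

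The cost is a short eCRF and SAE pathway and a small reporting burden at sites. No procedures or patients are added.

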AIM-HN enrolled subjects will receive tipifarnib administered at a dose of 600 mg, orally with a meal twice a day (bid) for 7 days in alternating weeks (Days 1-7 and 15-21) in 28-day cycles. Stepwise 300 mg dose reductions to control treatment-related, treatment-emergent toxicities are described in [Section 8.1.2](#). In the absence of unmanageable toxicities, subjects may continue to receive tipifarnib treatment until disease progression. If a complete response is observed, and subject continues to tolerate therapy, therapy with tipifarnib will be maintained for at least 6 months beyond the start of response.

Tumor assessment for the primary analysis will be performed by the IRF according to RECIST v1.1 and assessed by an Independent Data Monitoring Board (IDMB). Investigator assessment of tumor response will also be collected and reported as a supportive analysis. Assessments will be performed at screening and approximately every 8 weeks for the first 12 months of a subject's participation in AIM-HN; thereafter, tumor response assessment should occur approximately every 12 weeks until disease progression. Radiological assessments will be discontinued at the time of tumor progression. If the subject initiates a new anticancer therapy without evidence of

[figure not shown]
disease progression by RECIST v1.1, tumor scans should continue until there is evidence of disease progression unless withdrawal of subject's consent to study procedures. Local investigator evaluation of tumor assessment will guide on-study treatment decisions, including decisions to stop study treatment due to progressive disease.

Upon disease progression, all subjects will be followed approximately every 12 weeks for survival and the use of subsequent therapy until either death or End of Study (up to 2 years after the enrollment of the last study subject in AIM-HN, see [Section 6.7.1](#)), whichever occurs first.

All subjects will be followed-up for safety through the End of Treatment visit which occurs approximately 30 days after treatment discontinuation or immediately before the administration of another anticancer treatment, whichever occurs first. Additional safety follow-up may be conducted if unresolved toxicity is present at this End of Treatment visit. The IDMB will provide periodic evaluations of safety and other data to ensure adequate benefit/risk as well as the validity and scientific merit of the study.

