Serum chemistry ¹⁷	X ¹⁰	X ¹¹	X ¹⁸		X		
Hematology ¹⁷	X ¹⁰	X ¹¹	X ¹⁸		X		
Coagulation ¹⁷	X ¹⁰						
Urinalysis ¹⁹	X ¹⁰						
Radiographic Imaging, transfer of tumor scans and related clinical data to IRF ²⁰	X ¹³			X ²¹	X ²²	X ²³	
Tumor tissue for HRAS mutational testing and pathology confirmation at a central lab ^{31, 32}	X						

Tipifarnib administration ²⁸		X					
Drug accountability and diary review		X ¹⁶			X		
Collection of survival and anticancer treatment information ²⁹							X
QoL questionnaires ³⁴	X	X			X		

1. Screening evaluations will be completed within 4 weeks (28 days) of Cycle 1 Day 1. Evaluations performed as part of the standard of care within 28 days of dosing (prior to study specific consent signature) do not need to be repeated.
2. Tumor response assessment should occur approximately every 8 weeks (± 5 days) for the first 12 months of a subject's participation in AIM-HN; thereafter, tumor response assessment should occur approximately every 12 weeks (± 5 days) until disease progression.
3. An End of Treatment visit will be conducted approximately 30 days (± 7 days) from the last dose of tipifarnib or immediately before the initiation of any other anticancer therapy, whichever occurs first.
4. Follow up visit required only for subjects who terminated treatment for reasons other than disease progression and should occur approximately every 8 or 12 weeks (± 5 days) until disease progression.
5. Demographics and disease history including primary diagnosis (date of initial diagnosis, stage of disease at diagnosis, anatomical disease site(s) at diagnosis), current stage of disease, smoking and betel nut exposure history, alcohol use, HPV status and other relevant medical history.
6. Prior anti-cancer therapy for HNSCC including name, dates (start, end), treatment outcome (response and response criteria), duration of response, date of progression. Additionally, information will be collected specific to first line systemic treatment for recurrent or metastatic HNSCC. Information will also be collected on prior cancer surgery for HNSCC including date(s) of surgery. Information will be collected on prior/current radiological treatments for HNSCC including anatomical site(s) and date(s) of radiation treatment.

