11.5 Adverse Event Follow-up

All subjects will be followed-up for safety through approximately 30 days after treatment discontinuation or until immediately before the administration of another anticancer treatment, whichever occurs first. Additional safety follow-up may be conducted if unresolved toxicity is present at the End of Treatment visit. The IDMB will provide periodic evaluations of safety and other data to ensure subject safety as well as the validity and scientific merit of the study.

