12.1.2 Safety and Tolerability

Safety and tolerability of tipifarnib will be assessed based on the following:

- Incidence, duration, and severity of treatment-emergent AEs, SAEs, AEs resulting in permanent discontinuation of study drug, and deaths within approximately 30 days from the last dose of study drug (or immediately before the administration of another anti-cancer treatment)
- Changes in laboratory test results
- Changes in vital signs including blood pressure, heart rate and temperature
- Changes in ECG results

AEs will be coded using the using version 22.0 of the Medical Dictionary for Regulatory Activities (MedDRA) and upversioned prior to database lock. Treatment-emergent AEs are defined as AEs that start on or after the first dose of study drug and within approximately 30 days of the last administration of study drug. AEs will be summarized by the number and percentage of subjects who experienced the event, according to system organ class and preferred term. A subject reporting multiple cases of the same AE will be counted once within each system organ class and similarly counted once within each preferred term.

Unless specified otherwise, the denominator for these calculations will be based on the number of subjects enrolled who received at least one administration of tipifarnib, irrespective of the total number of doses or treatment cycles administered. These conventions will be appropriately modified to calculate AE incidence rates separately for each cycle that study therapy is administered. AE incidence rates may also be calculated based on other measures of subject exposure (e.g., total number of treatment cycles administered). AEs will also be summarized by NCI CTCAE v5.0 severity grade and by relationship to each study drug. Additional summaries may also be provided for SAEs, and events resulting in the permanent discontinuation of therapy. All AEs will be included in individual subject listings.

The incidence of grade 3 and 4 hematological toxicities (including neutropenia, thrombocytopenia, and anemia) will be provided by treatment cycle and across all treatment cycles. The toxicity grades for laboratory tests will be based on NCI CTCAE v5.0. The use of blood transfusions (platelets, red blood cells) and/or growth factor support will be reported.

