### 9.8.1 Adverse Events

All summaries of AEs will be based on treatment-emergent AEs (TEAEs) unless otherwise indicated.

TEAE is defined as AE that starts on or after the first dose of the study drug and within 30 days of the last administration of the study drug.

Counting of AEs will be by subject, not by event; subjects will be counted only once within each SOC or PT.

The count and percentage of subjects who report TEAEs will be summarized for AIM-HN safety analysis set as follows:

TEAEs by SOC and PT

TEAEs by PT (Any Grade and Grade  $\geq$  3)

TEAEs by SOC, PT, and maximum NCI-CTCAE grade

Serious TEAEs by SOC and PT

TEAEs related to tipifarnib by PT (Any Grade and Grade  $\geq$  3)

TEAEs related to tipifarnib by SOC, PT, and maximum NCI-CTCAE grade

Serious TEAEs related to tipifarnib by SOC and PT

TEAEs leading to discontinuation of tipifarnib by SOC and PT

TEAEs with an outcome of death by SOC and PT

Non-Serious TEAE experienced by  $\geq$  5% of subjects by PT

For grade summaries, subjects with multiple events within a particular SOC or PT will be counted under the category of their most severe event within that SOC or PT. Events will be sorted by descending frequency by SOC, and by PT within SOC for summaries.

AEs will be listed for individual subjects, including information regarding onset, duration, severity, seriousness, outcome and relationship to study drug.

AEs will not be summarized by Cycle, except for Overall Summary and AEs by SOC and PT for Cycle 1.

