## 9.8.4 Vital Signs

Body temperature will be summarized in °C. If body temperature is recorded as °F, then temperature will be converted to °C using:

$$\text{Temperature (°C)} = 5/9 (\text{Temperature [°F]} - 32).$$

Summaries of post baseline abnormal vital signs, including systolic blood pressure, diastolic blood pressure, pulse rate, weight change, and temperature will be presented. Abnormal ranges for vital signs parameters are given in [Table 3](#). Post baseline includes non-missing records from both scheduled and unscheduled visits after the first dose of study drug until 30 days following the last dose of study treatment.

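### The SAP's treatment-emergent AE window does not stop at the next anticancer therapy, although the protocol's AE reporting period does

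*Protocol*

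**What the plan says.** The documents contain two safety windows.

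**Closed by the next therapy.**
- The protocol synopsis and SAP 5.1 follow subjects for safety until the End of Treatment visit, placed at "approximately 30 days after treatment discontinuation or immediately before the administration of another anticancer treatment, whichever occurs first".
- Protocol 6.2.1 and 11.5 set the same 30-day follow-up with the limit "or until immediately before the administration of another anticancer treatment, whichever occurs first".
- Protocol 11.3.1 defines the AE reporting period as about 30 days from the final dose "or immediately before initiation of any other anticancer therapy, whichever comes first". Protocol 11.2 ties AE data collection to that reporting period.
- Table 2 footnote 3 times the End of Treatment visit at about 30 days from the last dose "or immediately before the initiation of any other anticancer therapy, whichever occurs first".
- The first bullet of Protocol 12.1.2 bounds the safety assessment by "deaths within approximately 30 days from the last dose of study drug (or immediately before the administration of another anti-cancer treatment", and the bracket closes there.

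**Not closed by the next therapy.**
- Table 2 footnote 9, on the AE row of the schedule: "Assessed from signing the AIM-HN ICF through approximately 30 days after treatment discontinuation".
- The sentence in Protocol 12.1.2 that defines a TEAE, which uses about 30 days after the last dose.
- The on-treatment period for safety variables in SAP 7, which runs 30 days past the last dose.
- The TEAE definition in SAP 9.8.1: "within 30 days of the last administration of the study drug".
- The vital-sign window in SAP 9.8.4: "until 30 days following the last dose of study treatment".

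SAP 9.8.1 builds its AE summaries on TEAEs unless it says otherwise. The visible text has no step that sets aside events starting after a new anticancer therapy.

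**The concern.** A subject may stop tipifarnib and start another regimen within 30 days. The repeated earlier-of wording shows that the authors expected this. An AE that begins on the new regimen is outside the protocol's reporting period but meets the SAP's TEAE definition. If it is in the database, it is tabulated with the tipifarnib events.

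Safety and tolerability is a secondary objective of a single-arm study, so no control group helps the reader separate the two sources. Capture may also be uneven: a site working from 11.3.1 has no duty to record such an event, while a site relying on footnote 9 might. Under 11.3.2 the duty to report a new SAE depends on the same reporting period.

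The SAP is also uneven across data types. The laboratory shift tables in SAP 9.8.3 stop at the End of Treatment visit, whereas the AE window does not.

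**Working it through.** The plan states no figure on this point, so there is nothing to reproduce. The check is a comparison of the texts, with one line of arithmetic.

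**1. One event under each rule.** Let the next therapy start on day *d* after the last tipifarnib dose, and let an AE start on day *t*, with *d* < *t* ≤ 30.

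| Source | Is the event inside the window? |
|---|---|
| Protocol 11.3.1 and 11.5, synopsis, 6.2.1 | No |
| Protocol 12.1.2, first bullet | No |
| SAP 5.1 (follow-up) | No |
| Table 2 footnote 9 | Yes |
| Protocol 12.1.2, TEAE sentence | Yes |
| SAP 7 and SAP 9.8.1 | Yes |

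Protocol 12.1.2 gives both answers within one section. The SAP caps follow-up in 5.1 but not the TEAE window in 9.8.1. The 30 days are exact in the SAP and approximate in the protocol.

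**2. Length of the overlap.** Without the limit, 30 − *d* days on the next therapy fall inside the TEAE window. The documents give no *d*. For assumed values of 7, 14 and 21 days:
- 30 − 7 = 23 days
- 30 − 14 = 16 days
- 30 − 21 = 9 days

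With the limit, the overlap is 0 days. These are lengths of window, not numbers of events.

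**3. How such an event could reach the database.** In Table 2 the last routine AE assessment is the End of Treatment visit, which footnote 3 places before the new therapy for an early switcher. After that:
- Subjects who have progressed move to Follow Up Contact, which has no AE entry and collects survival and subsequent treatment (Table 2; 9.2.9).
- Subjects who stopped for another reason have Follow Up Visits, where AE assessment is optional and applies if AEs were unresolved at End of Treatment (footnotes 4 and 8; 9.2.8).
- Unscheduled reports remain possible, as does recording by a site that takes footnote 9 at face value.

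Capture is therefore incidental, but it is not excluded.

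**4. Which tables would move.** A recorded event enters the all-causality TEAE tables and, according to its grade, seriousness and outcome, the Grade 3 or higher, serious and fatal ones. SAP 9.8.1 counts subjects, not events, so a row changes only if the subject was not already counted in it. The tipifarnib-related tables change only if the investigator judges the event related (11.3.1; 11.4.1).

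**5. What the size would require.** For one table row:

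change in percentage = P(switch before day 30) × P(qualifying event in the overlap, given a switch) × P(recorded, given the event) × P(not already counted, given a recorded event)

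The documents give none of these four terms.

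**The case against.** The strongest reply is that the protocol does indicate which window governs collection. Section 11.2 refers AE reporting to the period that 11.3.1 defines with the limit, and 11.5 repeats it. Footnote 9 is then a short schedule note, and the SAP definition acts on whatever was collected under the capped rule. One can add that an uncapped 30-day window is the cautious choice for all-causality safety, because it cannot lose a delayed tipifarnib effect.

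Most of this stands, and it rules out several stronger readings that a reader might infer:
- **That sites will systematically record next-line toxicity for the rest of the 30 days.** The schedule has no visit for this, and progressing subjects have no AE entry after End of Treatment.
- **That the tipifarnib AE rates are inflated by a definite number of percentage points.** Any such number would rest wholly on assumed switching shares and event rates. It would also have to allow for limited capture and for counting by subject.
- **That next-line toxicity will be reported as caused by tipifarnib.** The related-event tables depend on investigator causality.
- **That the SAP and footnote 9 stand against an otherwise consistent protocol.** Protocol 12.1.2 and the SAP each differ internally.
- **That the vital-sign window is a material problem.** Table 2 schedules no vital signs after End of Treatment, so few or no post-switch readings would fall in it.

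The objection does not remove the mismatch. If 11.3.1 governs collection, the analysis definition should follow it. As written, events that the protocol does not ask for are counted whenever they happen to be recorded, and that may depend on the site.

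**Conclusion.** The inconsistency holds and should be corrected, but it is modest. The AE reporting period ends at the next anticancer therapy; the TEAE definition that drives the AE tables does not. Post-switch events within 30 days of the last dose are therefore tabulated if recorded, although nothing in the schedule collects them systematically.

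The effect is confined to the all-causality TEAE tables and their Grade 3 or higher, serious and fatal subsets, unless an investigator attributes an event to tipifarnib. The objective response rate analysis is unaffected.

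The size cannot be estimated because the documents give no time to next therapy and no rate of post-switch capture. That it is probably small is a judgement from the visit schedule, and it assumes that sites generally work to 11.3.1.

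**What to change.** Before database lock:
- In SAP 9.8.1, and in the on-treatment period of SAP 7, end the window at 30 days after the last dose or at the start of another anticancer therapy, whichever occurs first. This matches Protocol 11.3.1.
- List any recorded AE that starts after that date, flagged as occurring after new therapy.
- State how an AE starting on the same date as the new therapy is classed, and how an incomplete subsequent-therapy date is handled. SAP 8.1.1 covers only AE and concomitant medication dates.
- Reconcile Table 2 footnote 9 and the TEAE sentence in Protocol 12.1.2 with 11.3.1.
- Align SAP 9.8.4 for consistency, with little practical effect expected.

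The cost is a clause in each place and one date comparison in programming. Start dates of subsequent therapy are already collected (Table 2 footnote 29; 9.2.8; 9.2.9). The downside is that a late tipifarnib effect starting after the switch would leave the summary tables and appear only in the flagged listing.
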